### **18.4 Missing Date of Investigational Product**

When the date of the last dose of IP is missing for a subject in any Part of the study, all efforts should be made to obtain the date from the investigator. If it is still missing after all efforts, then the last visit date when IP was returned will be used in the calculation of treatment duration.

### **18.5 Missing Date Information for Prior or Concomitant Medications**

For prior or concomitant medications, incomplete (ie, partially missing) start date and/or stop date will be imputed. When the start date and the stop date are both incomplete for a subject, impute the start date first.

#### **18.5.1 Incomplete Start Date**

The following rules will be applied to impute the missing numerical fields. If the stop date is complete and the imputed start date is after the stop date, then the start date will be imputed using the stop date.

#### **Missing day and month**

- If the year of the incomplete start date is the same as the year of the date of the first dose of IP, then the day and month of the date of the first dose of IP will be assigned to the missing fields.
- If the year of the incomplete start date is before the year of the date of the first dose of IP, then December 31 will be assigned to the missing fields
- If the year of the incomplete start date is after the year of the date of the first dose of IP,

then 01 January will be assigned to the missing fields.

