### 11.1 Adverse Events

Onset day of an AE is calculated as (start date of the AE - date of the first dose of IP) + 1. AEs will be classified into system organ class (SOC) and preferred term (PT) using Version 16.1, of MedDRA, to be determined closer to the conclusion of data collection.

An AE that occurs during the study will be considered a treatment emergent AE (TEAE) if it has a start date on or after the first dose of IP. TEAEs will be allocated to Part 1, Part 2, or Part 3, based on the onset date of the AE relative to the date and Part of the most recently administered IP. If an AE occurred more than 3 weeks after the date of the most recent IP, it will not be considered a TEAE. In the case of increases in severity, if there is more than 1 reference AE with the same preferred term then the AE with the greatest severity will be used as the benchmark for comparison to the AEs occurring in each Part of the study.

**Part 1:** An overall summary (**Table 4.2.1.1**) and summary by age group (**Table 4.2.1.2**) of the number of subjects in Safety Analysis Set 1 with TEAEs in Part 1 will be presented, including the number and proportion of subjects with any TEAEs, serious TEAEs, TEAEs related to lanthanum carbonate, TEAEs leading to study withdrawal, and TEAEs leading to death. The number of events, incidence, and percentage of TEAEs will be presented by SOC, and by preferred term (**Table 4.2.2.1**); by SOC, preferred term, and maximum severity (**Table 4.3.1.1**); and by SOC, preferred term, and relationship to lanthanum carbonate (**Table 4.3.2.1**). Similar summaries by SOC and preferred term will be produced for SAEs (**Table 4.4.1.1**), for deaths (**Table 4.4.2.1**), and for TEAEs leading to study withdrawal (**Table 4.4.3.1**). AEs (**Listing 7.1**), SAEs (**Listing 7.2**), AEs related to lanthanum carbonate (**Listing 7.3**), AEs leading to study withdrawal (**Listing 7.4**), and deaths (**Listing 7.5**) will be listed. AEs related to bone disease (preferred terms: adynamic bone disease and long bone fracture) are of special interest and will be summarised by SOC and preferred term (**Tables 4.5.1.1 and 4.5.2.1**) and listed separately (**Listing 7.6**).

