Only Part 2 will be summarised by treatment group (Calcium Carbonate and Lanthanum Carbonate) for the Safety Analysis Set 2 population summary.

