**Missing day only**

- If the month and year of the incomplete start date are the same as the month and year of the date of the first dose of IP, then the day of the date of the first dose of IP will be assigned to the missing day
- If either the year is before the year of the date of the first dose of IP or if both years are the same but the month is before the month of the date of the first dose of IP, then the last day of the month will be assigned to the missing day
- If either the year is after the year of the date of the first dose of IP or if both years are the same but the month is after the month of the date of the first dose of IP, then the first day of the month will be assigned to the missing day.

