### **18.6.1 Incomplete Start Date**

Follow same rules as in Section [18.5.1](#).

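### The rule for partial adverse-event start dates can re-date lanthanum-period events into the calcium period for subjects who entered Part 2a directly

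*SAP*

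**What the plan says.** For AEs with an incomplete start date, SAP 18.6.1 gives one instruction: "Follow same rules as in Section" 18.5.1, which is the rule for prior and concomitant medications. That rule works as follows.

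- Day and month missing, year equal to the first-dose year: "then the day and month of the date of the first dose of IP will be assigned to the missing fields".
- Day and month missing, later year: "then 01 January will be assigned to the missing fields".
- Only the day missing, same month as the first dose: the first-dose day is used.
- Only the day missing, later month or year: "then the first day of the month will be assigned to the missing day".
- The only guard concerns the stop date: "If the stop date is complete and the imputed start date is after the stop date, then the start date will be imputed" from the stop date.

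The first dose is not tied to a product, Part or treatment period. Calcium carbonate is an investigational product in Part 2a (Protocol 6.1) and always precedes lanthanum there (SAP 2.1).

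SAP 11.1 then allocates treatment-emergent AEs to Parts "based on the onset date of the AE relative to the date and Part of the most recently administered IP". It adds: "Only Part 2 will be summarised by treatment group (Calcium Carbonate and Lanthanum Carbonate) for the Safety Analysis Set 2 population summary". Separate tables pool Parts 2 and 3 for lanthanum only. SAP 4.3.2 counts events under calcium until lanthanum is received.

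**The concern.** A first-dose anchor suits a study with one treatment: an event of uncertain onset is counted as treatment-emergent. In a fixed calcium-then-lanthanum sequence the same anchor also decides which drug the event is charged to, and for direct Part 2a entrants it points to the comparator. Reading the phrase as the first dose in the relevant Part does not help, because the first Part 2 dose in Part 2a is still calcium.

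The safety profile is the first secondary objective, and SAP 2.5 says the study's focus was shifted to safety. That section justifies 32 subjects by an 80.6% chance of seeing at least one event with a 5% rate (1 − 0.95^32 = 0.806). The expected count is 32 × 0.05 = 1.6, and the chance of exactly one is 32 × 0.05 × 0.95^31 = 33%. If that single event came from a direct Part 2a entrant and had a partial date, re-dating it could empty the lanthanum row.

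The direction also differs from the SAP's other choices. For AEs starting on or after first dose, missing severity becomes severe (18.7) and missing relationship becomes related (18.8). Elsewhere the SAP does name its anchor: prior medication uses the first intake in the relevant Part, and concomitant medication in Parts 2 and 3 combined uses the first lanthanum dose (SAP 9).

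**Working it through.** The plan states no figure on this point, so there is nothing to reproduce. The check applies the rules of 18.5.1 to every possible calcium start date.

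**Inputs.** From the documents: calcium for 56 days, washout w of 0 to 21 days, lanthanum for 56 days in Period 2, and Part 3 from Week 16 to Week 40 (24 weeks), giving 224 lanthanum days. Assumed: the first calcium dose F is equally likely on each of 365 days, and true onset is even over the lanthanum days. The first lanthanum dose is L = F + 56 + w.

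**Direction, direct Part 2a entrants.** For an onset on or after F, each rule returns the earliest date that fits the partial date and is not before F. The imputed date is therefore never later than the true one, and the stop-date guard can only move it earlier still. A lanthanum event can fall back before L; a calcium event cannot move forward past L. A date falling in the washout is at most 21 days after the last calcium dose, so it still counts under calcium.

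**Only the day missing.** After a full 8-week calcium period, L is at least 56 days after F, so no lanthanum onset shares a month with F and the first-dose rule is never reached. The first-of-month rule re-dates an event before L when onset falls in the calendar month of L and L is not the 1st. In a month of m days, the affected onset days, summed over all positions of L, are m(m − 1)/2:

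- 7 × 465 + 4 × 435 + 378 = 5,373 over the year
- 5,373/365 = 14.7 affected days per subject
- Period 2: 14.7/56 = 26%
- 32 weeks: 14.7/224 = 7%

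**Day and month missing.** An event stays with lanthanum only if L is on or before a 1 January that follows F and onset is on or after that date. With D lanthanum days, the share that stays is [D(D + 1)/2]/(365 × D) = (D + 1)/730.

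- Period 2: 57/730 = 7.8% stay, 92% re-dated
- 32 weeks: 225/730 = 30.8% stay, 69% re-dated

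The first-dose rule covers the Period 2 events whose onset is in the same year as F. The mean offset from F is 56 + w + 27.5 days, so the share is (365 − 83.5)/365 = 77% without washout and (365 − 104.5)/365 = 71% with three weeks. The rest of the 92% comes from the 01 January rule.

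**Part 1 participants.** Their first product is the Part 1 lanthanum dose, assumed here to be 2 days before F. Enumerating all start dates for year-only dates, 71% to 77% of Period 2 lanthanum events go to the Part 1 dose and 15% to 21% to calcium, while 92% of calcium events go to the Part 1 dose. With only the day missing, 26% of calcium events go to Part 1.

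**Part 2b.** There is no calcium exposure, so the shift to calcium is 0%.

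**The case against.** The strongest reply is that few dates will be affected. Protocol 7.2.3.3 asks about AEs since the previous visit, visits are two-weekly in Part 2 and monthly in Part 3, and omissions are queried (Protocol 9.2). A year-only onset should then be rare. That is fair: the day-missing figures are the ones to lead with, and the 92% and 69% describe the less likely case. It does not remove the fault, because the rule exists for whatever partial dates remain.

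A second reply is that imputing to the first dose is a standard conservative choice. It is, for deciding whether an event is treatment-emergent. It is not for deciding between two products in a fixed order.

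Three stronger readings are tempting, and the documents do not support them.

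- A reader might infer that every imputation moves an event earlier. Partial dates in an earlier year go to 31 December and those in an earlier month to its last day. A true pre-dose event dated only to the first-dose year or month is moved later, to the first dose. AEs are collected from consent, so such events can occur.
- A reader might infer that errors run only from lanthanum to calcium across the study. That holds for direct Part 2a entrants. In Part 1 participants, calcium events can be drawn onto a lanthanum dose.
- A reader might infer that lanthanum safety as a whole is understated. All subjects newly enrolled under protocol Version 6.0 enter Part 2b and cannot lose events to calcium.

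**Conclusion.** The rule is wrong as written, limited to Part 2a subjects. In direct Part 2a entrants it favours the test drug: lanthanum-period AEs can be lost to calcium and none are gained. In Part 1 participants it also misattributes, but towards Part 1 and from both treatments.

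The percentages are shares of AEs with that kind of partial date, not of all AEs. They rest on even spreads of onset and calcium start and on a full 8-week calcium period. Subjects who left calcium early for Part 3 because of hypercalcemia were not modelled; with a short calcium period, their day-missing dates could also reach the first-dose rule. With the number of partial dates unknown, this should be corrected in the SAP, but it is not evidence that the lanthanum safety results will be materially distorted.

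**What to change.** Replace the cross-reference in SAP 18.6.1 with an AE-specific rule:

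1. Bound the onset by the partial date, any stop date, and the interval between the visit at which the AE was first recorded and the previous visit.
2. If that interval lies within one treatment period (Part 1, Part 2a calcium, Part 2a lanthanum, Part 2b or Part 3), impute no earlier than the first dose of that period.
3. If it still spans the calcium-to-lanthanum switch, assign the AE to lanthanum in the main table, dated to the first Part 2 or Part 3 lanthanum dose. List it, and show the alternative attribution to calcium.

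Naming the Part 2 or Part 3 dose matters, because a Part 1 participant's first lanthanum dose precedes calcium. Step 1 assumes that the recording visit can be identified in the data. Protocol Table 1 schedules AE recording both at Visit 2.4 and at washout W2, where lanthanum is dispensed, so few AEs should reach step 3.

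A shorter rule that sends every compatible date to lanthanum would overcorrect. For year-only dates, the calcium events incompatible with lanthanum onset are 1,596/(365 × 56) = 7.8% without washout and (1,596 + 21 × 56)/(365 × 56) = 13.6% with three weeks (1,596 = 56 × 57/2). So 86% to 92% of true calcium events would move unless a stop date ruled it out. With only the day missing it would be 2% (three-week washout) to 26% (none).

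The cost is a short SAP paragraph, a little extra programming, and a few AEs of uncertain onset around the switch counted under lanthanum. No new data are needed if the recording visit is held.

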**Missing month only**

- The day will be treated as missing and both month and day will be replaced according to the above procedure.

**Missing day only**

- If the month and year of the incomplete start date are the same as the month and year of the date of the first dose of IP, then the day of the date of the first dose of IP will be assigned to the missing day
- If either the year is before the year of the date of the first dose of IP or if both years are the same but the month is before the month of the date of the first dose of IP, then the last day of the month will be assigned to the missing day
- If either the year is after the year of the date of the first dose of IP or if both years are the same but the month is after the month of the date of the first dose of IP, then the first day of the month will be assigned to the missing day.

**18.5.2 Incomplete Stop Date**

The following rules will be applied to impute the missing numerical fields. If the date of the last dose of IP is missing, then replace it with the last visit date. If the imputed stop date is before the start date (imputed or non-imputed start date), then the imputed stop date will be equal to the start date.

**Missing day and month**

- If the year of the incomplete stop date is the same as the year as of the date of the last dose of IP, then the day and month of the date of the last dose of IP will be assigned to the missing fields
- If the year of the incomplete stop date is before the year of the date of the last dose of IP, then 31 December will be assigned to the missing fields
- If the year of the incomplete stop date is after the year of the date of the last dose of IP, then 01 January will be assigned to the missing fields.

**Missing month only**

- The day will be treated as missing and both month and day will be replaced according to the above procedure.

**Missing day only**

- If the month and year of the incomplete stop date are the same as the month and year of the date of the last dose of IP, then the day of the date of the last dose of IP will be assigned to the missing day
- If either the year is before the year of the date of the last dose of IP or if both years are the same but the month is before the month of the date of the last dose of IP, then the last day of the month will be assigned to the missing day
- If either the year is after the year of the last dose of IP or if both years are the same but the

month is after the month of the date of the last dose of IP, then the first day of the month will be assigned to the missing day.

## **18.6 Missing Date Information for Adverse Events**

For AEs, the default is to only impute incomplete (ie, partially missing) start dates. Incomplete stop dates may also be imputed when calculation of the duration of an AE is required per the protocol. If imputation of an incomplete stop date is required, and both the start date and the stop date are incomplete for a subject, impute the start date first.

### **18.6.1 Incomplete Start Date**

Follow same rules as in Section [18.5.1](#).

### **18.6.2 Incomplete Stop Date**

When required per the protocol, follow the same rules as in Section [18.5.2](#).

## **18.7 Missing Severity Assessment for Adverse Events**

If severity is missing for an AE starting prior to the date of the first dose of IP, then a severity of “Mild” will be assigned. If the severity is missing for an AE starting on or after the date of the first dose of IP, then a severity of “Severe” will be assigned. The imputed values for severity assessment will be used for incidence summaries, while the actual values will be used in data listings.

## **18.8 Missing Relationship to Investigation Product for Adverse Events**

If the relationship to IP is missing for an AE starting on or after the date of the first dose of IP, a causality of “Related” will be assigned. The imputed values for relationship to double-blind IP will be used for incidence summaries, while the actual values will be presented in data listings.

## **18.9 Character Values of Clinical Laboratory Variables**

If the reported value of a clinical laboratory endpoint cannot be used in a statistical analysis due to, for example, that a character string is reported for a numerical endpoint, the appropriately determined coded value will be used in the statistical analysis. However, the actual values as reported in the database will be presented in data listings. Coding of special character values will be determined before the database lock.

## 21. APPENDIX

### 21.1 Evaluable Subject Determination Plan

#### 1. Definition of Evaluable Subject in Per-Protocol Analysis Set 2 for Primary Endpoint Assessment

For the purposes of the primary endpoint assessment, at least 32 subjects, who complete 8 weeks of treatment with lanthanum carbonate and are assessable for baseline and 8 weeks serum phosphate level, will be required. Approximately 65 subjects may be enrolled to acquire at least 32 evaluable subjects. In order to prevent over enrolment, subjects' evaluability status will be assessed and confirmation of achieving at least 32 evaluable subjects will be performed.

The criteria that subjects must meet to determine eligibility include:

- Aged 10 years to <18 years of age at the time of consent
- Confirmed serum phosphorus level drawn prior to commencing Lanthanum therapy in Part 2 or Part 3 of the clinical trial (Baseline Phosphorus)
  - Subjects who participated in Part 2a and received calcium carbonate, baseline serum phosphorus must be drawn after a washout period of up to 3 weeks
- Baseline serum phosphorus levels above KDOQI recommendations:
  - Age <12 years: Serum phosphorus >6.0mg/dL (1.94mmol/L)
  - Age ≥12 years and older: Serum phosphorus >5.5mg/dL (1.78mmol/L)
- Demonstration of 8 weeks of Lanthanum therapy
- Confirmed serum phosphorus level after 8 weeks of Lanthanum therapy
- Both baseline and 8 weeks serum phosphorus levels are assessed at the same lab (central or local lab)
- Subjects, who received lanthanum carbonate therapy in part 2 or part 3 but did not receive 8 weeks of continuous treatment because of temporary dose interruption due to hypophosphatemia (protocol Appendix 2: guidelines for phosphorus and calcium levels), will be considered evaluable, if they satisfy other criteria mentioned above (eg baseline phosphate > KDOQI target).

#### 1.1 Data Variable Requirements

##### I. Subject Age

Age is calculated using Informed Consent Date minus Birth date. However, birth date may not be available in all cases (due to subject privacy concerns). When instead of birth date only birth year is entered in the clinical database, age will be imputed using June 30th of the year of birth. However, if the age falls below 10 years old or over 18 years old and inclusion criteria number 01 is met, we will consider the age-categories to confirm whether the age-criterion was met. KDOQI Target: Created based on age condition:

- If DM.AGE <12 years, then KDOQI Target = 1.94mmol/L
- If DM.AGE ≥12 years, then KDOQI Target = 1.78mmol/L

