## 7. DEMOGRAPHIC AND OTHER BASELINE CHARACTERISTICS

**Part 1:** Descriptive summaries will be presented for Lanthanum Carbonate for the Safety Analysis Set 1 (**Table 1.2.1.1.1**) and presented by age group ( $\geq 10$  to  $<12$  years,  $\geq 12$  to  $<18$  years). (**Table 1.2.1.1.2**)

**Part 2:** Descriptive summaries will be presented by treatment group for the Safety Analysis Set 2, the FAS, the PP1, the PP2 for lanthanum carbonate treatment only (Part 2a, Treatment Period 2 and Part 2b) additionally presented by age group ( $\geq 10$  to  $<12$  years,  $\geq 12$  to  $<18$  years) (**Table 1.2.1.2.1 to Table 1.2.1.4.2 and Table 1.2.1.5.1 and Table 1.2.1.5.2, respectively**).

**Part 2 and 3 Combined (Lanthanum Carbonate only):** Descriptive summaries will be presented for Lanthanum Carbonate for the SCS for 8 weeks of lanthanum carbonate treatment only, (**Table 1.2.1.6.1**) additionally presented by age group ( $\geq 10$  to  $<12$  years,  $\geq 12$  to  $<18$  years). (**Table 1.2.1.6.2**)

**Pharmacokinetic Set 1:** Descriptive summaries will be presented for PK Set 1 (**Table 1.2.1.7.1**), and additionally presented by age group ( $\geq 10$  to  $<12$  years,  $\geq 12$  to  $<18$  years). (**Table 1.2.1.7.2**)

**Pharmacokinetic Set 2:** Descriptive summaries will be presented for PK Set 2 (**Table 1.2.1.7.3**), and additionally presented by age group ( $\geq 10$  to  $<12$  years,  $\geq 12$  to  $<18$  years). (**Table 1.2.1.7.4**)

The following demographic characteristics will be summarised in the following order in the tables: age (years), age group (categorical:  $<10$  years,  $\geq 10$  to  $<12$  years,  $\geq 12$  to  $<18$  years and  $\geq 18$  years), sex, ethnicity, race, weight (kg), height (cm) and Body Mass Index ( $\text{kg}/\text{m}^2$ ). Continuous variables such as subject age, weight, and height will be summarised using number of observations, mean, standard deviation, median, minimum, and maximum values. Categorical variables such as the subject's sex, ethnicity, and race will be summarised using number of observations and percentages for each category. Please note that age will only be calculated when the date of birth is not partial. Age will be calculated as the difference between date of birth and date of informed consent or assent, which is usually signed at the beginning of the Screening Period.

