## 17. CHANGES TO ANALYSES SPECIFIED IN PROTOCOL

The following changes to the analyses as outlined in the Protocol Version 6.0 (Amendment 5), 18 Oct 2016 were as follows:

- Subject Disposition for Part 2 (2a and 2b) was proposed to be presented by Treatment group. However, the presentation will be presented by Parts 2a and 2b.
- The Safety Analysis Set 2 was redefined to include Part 3 (long-term safety); therefore, removed Safety Analysis Set 3 and added Safety Completer Set (SCS) to include subjects who received 8 weeks of lanthanum carbonate treatment from Part 2 or Part 3 of the study as a result of and in response to discussions with PDCO.
- An inconsistency in wording exists between the protocol Synopsis (under the Efficacy Analysis section on pages 29 and 30) and protocol Section 9.10.2 (Secondary Variables, page 80). The Synopsis wording states “For the long-term assessment, efficacy and safety variables will be summarized using the FAS and SAS2, respectively...” whereas the wording in Section 9.10.2 states “For the long-term assessment, efficacy and safety variables will be summarized using the Safety Analysis Set 2 for each visit using descriptive statistics...”. The wording will no longer appear in the text, but the SAP will more closely follow what appears in the protocol Synopsis and summarize long-term variables using the FAS analysis population.

The definitions of the FAS and SAS2 are identical except for a subsequent required assessment (ie, at least 1 phosphate assessment or the completion of at least 1 follow-up safety assessment, respectively). It is unlikely that a subject would complete a follow-up safety assessment without also having at least 1 phosphate assessment. As a result, if there is a difference in the size or quality between these 2 analysis populations it would be negligible and hence no impact on the summaries that will be provided.

- The age group categories that will be summarized within the Demographic and Baseline Characteristics tables has been updated from 2 categories (ie, <12 years and ≥12 years) to 4 categories (<10 years, ≥ 10 to <12 years, ≥12 to <18 years and ≥ 18 years) to account for the ages of all subjects who participated in the study across various versions of the protocol and age group categories that appear in the most recent and up-to-date CRF.

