## 1.2 Data Sources for Assessment of Evaluability

Evaluability Assessment will be performed on the subject level analysis data set (one record per subject) created through the steps described in section V.

Evaluability is determined if the following conditions are met

1. If subject is not a screen failure
2. Baseline Phosphate data is not missing, and baseline phosphate is  $\geq$  KDOQI Target
3. Week 8 Phosphate data is not missing

OR

Phosphate value missing at Week 8, but early termination shows hypophosphatemia (Protocol Appendix 2: guidelines for phosphorus and calcium levels).

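### For subjects with birth year only, SAP 21.1 sets the KDOQI target from an age imputed to 30 June with no check at 12, so some who turn 12 in the consent year can get the wrong PP2 baseline threshold and Week 8 target

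*SAP*

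**What the plan says.** SAP 21.1, I. Subject Age, defines age as consent date minus birth date and allows that some birth dates may be withheld for privacy. In that case, where "only birth year is entered in the clinical database, age will be imputed using June 30th of the year of birth". One safeguard follows: "if the age falls below 10 years old or over 18 years old and inclusion criteria number 01 is met, we will consider the age-categories". The target is then assigned by age: "If DM.AGE <12 years, then KDOQI Target = 1.94mmol/L" and "If DM.AGE ≥12 years, then KDOQI Target = 1.78mmol/L". These equal 6.0 and 5.5 mg/dL.

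The target is used in SAP 21.1, 1.2 Data Sources for Assessment of Evaluability. The condition there begins "Baseline Phosphate data is not missing, and baseline phosphate is" and continues with a comparison against the KDOQI target. SAP 10.1 makes PP2 the primary analysis population and scores the Week 8 response against the age-specific target. It gives no derivation of its own for partial birth dates, and SAP 18.2 (Derived Efficacy Endpoints) is marked not applicable.

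Two other places bear on this. SAP 7 says: "Please note that age will only be calculated when the date of birth is not partial". SAP 17 describes four demographic age groups, with a split at 12, chosen partly to match the "age group categories that appear in the most recent and up-to-date CRF". Protocol 4.1, inclusion criterion 5, sets the trial-entry phosphorus threshold by age and has no imputation rule.

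**The concern.** The SAP accepts that an imputed age can be wrong and provides a check for it, but at 10 and 18 rather than at 12. A subject on the wrong side of 10 or 18 after imputation is rescued by the category. A subject on the wrong side of 12 is not, and that subject's threshold and target change.

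What can go wrong depends on the direction:

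- **Truly 12, imputed 11.** The target becomes 6.0 instead of 5.5 mg/dL. A validly enrolled subject with a baseline between the two values can be dropped from PP2. One who stays in PP2 with a Week 8 value between them is scored a success against the wrong target.
- **Truly 11, imputed 12.** The target becomes 5.5 instead of 6.0 mg/dL. A Week 8 value between them meets the child's own target but is scored a failure. PP2 membership is seldom affected, because treatment normally started only above 6.0.

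SAP 21.1 also uses evaluability to confirm that 32 evaluable subjects have been reached. In addition, SAP 17 says the by-age tables are aligned with the age groups used for the endpoints. With one age rule in SAP 7 and another in SAP 21.1, that alignment is not assured for these subjects.

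**Working it through.** The documents give no figure for age misclassification. The evaluable number used below is the SAP's 32 (SAP 2.5). Its stated 80.6% reproduces: 1 − 0.95^32 = 0.806.

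Inputs from the documents: imputation to 30 June, target cut at 12, eligible ages 10 to <18, targets 6.0 and 5.5 mg/dL, n = 32. Assumptions not in the documents: true ages uniform over 10 to <18, and birth and consent dates uniform over the year. The share with birth year only is unknown and is varied.

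1. **Who can be affected.** The imputed date is in the right calendar year, so the error is at most about half a year. True and imputed age can fall on different sides of 12 only if the 12th birthday lies in the calendar year of consent.

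2. **Chance within that group.** Let c and b be the consent and birth dates as fractions of the year, with 30 June at about 0.5. Imputed age is at least 12 if c ≥ 0.5; true age is at least 12 if b ≤ c. For c < 0.5 the error probability is c; for c ≥ 0.5 it is 1 − c. The average of min(c, 1 − c) over the year is 0.25. It is about 4% for consent in January or December and about 46% in June or July.

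3. **Share of all birth-year-only subjects.** One birth-year cohort out of eight is 1/8 = 0.125, and 0.125 × 0.25 = 0.031. A simulation of 4 million such subjects gave 3.1%: about 1.6% truly 11 imputed 12, and about 1.5% truly 12 imputed 11.

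4. **Two worked cases.** True age 12.1, consent in mid-March (c about 0.2): imputed age 12 + 0.2 − 0.5 = 11.7, so a baseline of 5.8 mg/dL fails the PP2 threshold. True age 11.8, consent in mid-September (c about 0.7): imputed age 12 + 0.7 − 0.5 = 12.2, so a Week 8 value of 5.8 is scored a failure.

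5. **Expected number misclassified among 32.**

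| Birth-year-only share (assumed) | Expected number | Chance of at least one |
|---|---|---|
| 100% | 32 × 0.031 = 1.0 | 64% |
| 50% | 0.5 | 40% |
| 25% | 0.25 | 22% |

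   If 5% to 40% of subjects, rather than 12.5%, were in their turning-12 year, the 100% row would run from 32 × 0.25 × 0.05 = 0.4 to 32 × 0.25 × 0.40 = 3.2.

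6. **Expected number of changed results.** A wrong target matters only if phosphate is above 5.5 and up to 6.0 mg/dL. The documents give no share in that band. Assuming 10% to 30% at Week 8, and 25% to 100% with birth year only, expected Week 8 changes run from 0.25 × 0.10 = 0.025 to 1.0 × 0.30 = 0.30. PP2 exclusions come mainly from the truly-12 half. At the ceiling, with the same 30% assumed at baseline, they add about 0.5 × 0.30 = 0.15. The total stays below one.

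7. **Effect of one change.** 16/32 = 50.0% (exact 95% CI 31.9 to 68.1); 17/32 = 53.1% (34.7 to 70.9). The shift is 3.1 percentage points.

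**The case against.** The case for leaving this alone is substantial. The rule affects only subjects with birth year only, and the SAP suggests merely that some birth dates may be missing; the number could be near zero. Under the assumptions above, three quarters of those turning 12 are still assigned correctly. Errors run about equally in both directions, so at Week 8 they tend to cancel. The endpoint is descriptive, with no hypothesis test, and one changed responder is small beside an interval of roughly 32% to 68%. All of that stands, and it limits the size of the point.

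Three textual objections stand in part. First, the SAP never says outright that DM.AGE holds the imputed value, and the rule sits in the evaluability plan, so its use for Week 8 scoring is inferred. It is, however, the natural reading and the only target derivation given. Second, SAP 7 governs demographic summaries and could coexist with SAP 21.1; its result would be a missing age, not a different one. The two sections still disagree on whether age is calculated from a partial date. Third, the CRF categories are shown only for the most recent CRF, in a study that began in 2012 and ran under several protocol versions. A reader might infer that the correct category is already held for every subject and is being overridden; the documents do not show that.

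**Conclusion.** The point holds as a specific, avoidable weakness in a stated derivation rule. For birth-year-only subjects, the safeguard is missing at the one age that determines the target. About 25% of those turning 12 in the consent year, or 3.1% of all birth-year-only subjects, can be misassigned if ages and dates are uniform. At the ceiling where every subject has birth year only, that is about 1 of 32, with fewer than one changed result expected.

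A reader might infer that children near 12 generally get the wrong target. They do not: it takes birth year only, a 12th birthday in the consent year, and then an unfavourable combination of dates. A reader might also infer that trial entry is affected. It is not: inclusion criterion 5 is applied by age without imputation, and only the PP2 baseline threshold and the response target are exposed. The conflict between SAP 7 and SAP 21.1 needs resolving whatever the number of subjects.

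**What to change.** In SAP 21.1, I. Subject Age, state that when only birth year is held, the KDOQI target and the PP2 baseline threshold are set from the recorded CRF age category (≥10 to <12 or ≥12 to <18) wherever it is available, not only when the imputed age falls outside 10 to 18. Use the 30 June age only if no category split at 12 was recorded, for example under an earlier CRF version. Amend SAP 7 so that the demographic and by-age tables use the same category for these subjects.

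The cost is about two sentences in the SAP, one line of derivation code, and a check of whether the category is held for subjects enrolled under earlier CRF versions. No new data are needed where the category is recorded, and no sample-size figure changes. If the category is correctly recorded, misassignment at 12 falls to zero for those subjects.
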